**Table 1: REGN10933+REGN10987 Doses for Each Pediatric Weight-Tiered Groups**

Pediatric Weight-Tiered Groups	Route of Administration	Dose (mg)		Total Dose (mg)
		REGN10933	REGN10987	

≥40 kg	SC	600	600	1200
≥20 to <40 kg	SC	396	396	792
≥10 to <20 kg	SC	204	204	408
≥5 to <10 kg	IM	72	72	144
≥2.5 to <5 kg	IM	48	48	96
<2.5 kg	IM	24	24	48

A 4-week GLP toxicology study in cynomolgus monkeys was conducted and assessed once weekly dosing of up to 150/150 mg/kg per mAb administered once weekly (for combination) to support safety of the anti-SARS-CoV-2 spike mAbs. Throughout the 4-week dosing period the REGN10933+REGN10987 combination was well tolerated at all dose levels, with no drug-related or adverse effects evident (for more information, refer to the IB).

### 3.3. Risk-Benefit

This study represents the initial prophylaxis study planned to evaluate REGN10933+REGN10987 as a SC injection in humans. Therefore, the potential clinical benefits and risks associated with the study drugs are yet to be determined. Several preclinical pharmacokinetic, pharmacologic, and toxicology studies are ongoing and/or planned, and findings from these studies will be appropriately communicated. While preclinical data are available (discussed below), the anticipated risks are based primarily on prior Sponsor experience with similar fully human monoclonal antibody development programs against exogenous targets and the potential risks associated with subcutaneous injection of fully human monoclonal antibodies in general.

The positive efficacy results observed for REGN10933+REGN10987 administered IV to symptomatic patients with COVID-19 in R10933-10987-COV-2067 study are balanced by an acceptable safety profile. Nonclinical toxicology studies in nonhuman primates showed that REGN10933+REGN10987 was well-tolerated without adverse findings. Moreover, review of available clinical data from the 3 ongoing clinical studies (R10933-10987-COV-2066, R10933-10987-COV-2067, R10933+REGN10987-HV-2093) show that there are currently no identified risks with REGN10933+REGN10987. There are several potential risks, which are described below.

A 4-week GLP toxicology study in cynomolgus monkeys is currently ongoing and assessing once-weekly IV and SC dosing of REGN10933+REGN10987 at up to 150 mg/kg per antibody. Findings from the completed 4-week dosing period of the toxicology study identified no clinically relevant risks or test article-related adverse effects and no changes to reproductive organs in nonhuman primates. Separately, findings from 2 tissue cross reactivity studies was notable for by the absence of any tissue cross reactivity with either REGN10933 or REGN10987 in any of the human or monkey tissues or human fetal tissues evaluated. Reproductive and developmental toxicology studies have not been conducted; therefore, the effects of REGN10933, REGN10987, and REGN10933+REGN10987 combination therapy on the fetus and reproductive organs in males and females are unknown.

REGN10933 and REGN10987 target the SARS-CoV-2 S protein, an exogenous protein. The Sponsor has significant experience with prior development programs for fully human mAbs against exogenous targets, including atoltivimab, odesivimab, and mafostivimab (Ebola), REGN3048 and REGN3051 (MERS-CoV), REGN5713, REGN5714 and REGN5715 (Bet v 1

birch tree allergen), and REGN1908 and REGN1909 (Fel d 1 cat dander allergen). No significant safety findings were observed in any of the associated toxicology studies conducted and the mAbs demonstrated an acceptable safety profile in the clinical studies.

**Important Potential Risks:** The important potential risks are those typically associated with a mAb administered by SC route: injection site reactions, hypersensitivity reactions, immunogenicity, and potential embryo-fetal toxicity (see the IB). REGN10933 and REGN10987 are fully human IgG1 mAbs, and correspondingly the risk of injection site reactions, hypersensitivity reactions, or immunogenicity is expected to be low. However, given the limited experience with these mAbs and the evolving understanding of SARS-CoV-2 infections, all TEAEs will be collected during the study to adequately characterize the safety profile of REGN10933+REGN10987. Clinical safety and tolerability data from the pooled sentinel cohorts from treatment studies (R10933-10987-COV-2066 and R10933-10987-COV-2067) in COVID-19 patients receiving IV administration of REGN10933+REGN10987 were available prior to first SC dosing in this study. These data showed that a single IV dose of REGN10933+REGN10987 or placebo (at 1200 mg per mAb, at 4000 mg per mAb) was well-tolerated, with no hypersensitivity reactions or infusion-related reactions reported. Vital signs and laboratory assessments did not identify any safety signals (Section 3.2.4). Protein therapeutics carry the potential risk of an immunogenic response in the form of ADA and NAb development following administration, with possible consequences on safety and efficacy. Therefore, blood samples for immunogenicity assessment will be collected during the studies.

Reproductive and developmental toxicology studies have not been conducted; therefore, the effects of REGN10933, REGN10987, and REGN10933+REGN10987 combination therapy on the fetus and reproductive organs in males and females are unknown. Human immunoglobulin G1 (IgG1) antibodies are known to cross the placental barrier and are present in breast milk; therefore, the REGN10933+REGN10987 combination therapy have the potential to be transferred from the mother to the developing fetus or a breastfed child. Given the high affinity and specificity of REGN10933 and REGN10987, off-target pharmacological effects are not anticipated in either the mother, the fetus, or breastfed child and no off-target binding of REGN10933 or REGN10987 was observed in any of the human or monkey tissues evaluated ex vivo in tissue cross-reactivity studies. However, it is unknown whether the potential transfer of the combination of REGN10933+REGN10987 therapy provides any treatment benefit or risk to the developing fetus or breastfed child.

There is currently limited clinical experience in the use of REGN10933, REGN10987, and REGN10933+REGN10987 combination therapy in female subjects who are pregnant or breastfeeding. The combination of REGN10933+REGN10987 therapy should be used during pregnancy or breastfeeding only if the potential benefit justifies the potential risk for the mother and the fetus or breastfed child considering all associated health factors. If a female subject is pregnant or were to become pregnant while receiving REGN10933+REGN10987 combination, the pregnancy should be followed until outcome and any safety issue observed get reported.

**Other Theoretical Considerations:** Antibody-dependent enhancement (ADE) has also been observed for some therapeutics targeting exogenous viral proteins. For antibody therapies, ADE is thought to occur when binding of antibody to the target viral protein enhances Fc $\gamma$ R-mediated host cell entry of the virus (Iwasaki, 2020). This could potentially lead to worsening of disease and, in the case of SARS, acute lung injury (Liu, 2019). REGN10933 and REGN10987 retain the Fc

region, as this may play a role in protecting against viral infection (Yasui, 2014). However, there is no strong evidence of ADE in other coronavirus models (Kam, 2007) (Liu, 2019) (Luo, 2018) (Wang, 2016) (Weingartl, 2004). To date, Fc-containing mAbs developed by the Sponsor for Ebola virus, and MERS-CoV have demonstrated specificity to their exogenous targets with no significant unexpected safety findings in preclinical or clinical studies. All subjects will be monitored for TEAEs during the drug elimination period. Theoretical risks of administration of the REGN10933+REGN10987 combination include interference with the subject's endogenous immune response to either SARS-CoV-2 infection or vaccination against SARS-CoV-2.

With respect to efficacy, the currently available in vitro data (see the IB) show that REGN10933+REGN10987 is anticipated to be pharmacologically active at the planned dose, with expected neutralization and effector functions against the SARS-CoV-2 S protein. Additionally, the only control measures that are currently available against this virus is practicing rigorous infection control. There is no therapeutic option for the prevention of SARS-CoV-2 infection and there is an urgent need for a preventative treatment given the wide reaching, devastating effects of this global outbreak (Woodworth, 2020).

Emerging data suggest that the pediatric population is equally vulnerable to SARS-CoV-2 infection and may contribute significantly to transmission (Szablewski, 2020) (Lewis, 2020) (Viner, 2020) and that pregnant women are at increased risk for developing severe COVID-19 and have been shown to have a higher rate of hospitalization, need for mechanical ventilation, and ICU admission than non-pregnant women (Ellington, 2020) (Knight, 2020) (Woodworth, 2020). Neonatal transmission of SARS-CoV-2 has also been reported (Vivanti, 2020). Therefore, all adults and children should be considered for inclusion in COVID-19 prophylaxis efforts.

In summary, based on prior experience with other fully human mAbs against exogenous targets, the available clinical and nonclinical data for REGN10933+REGN10987 to date, and the unmet need for a preventative therapy in advance of an approved vaccine, it is the opinion of the Sponsor that the overall risk-benefit balance for REGN10933+REGN10987 is acceptable to allow evaluation of this mAb combination in all populations, including adults, pregnant and breastfeeding women, and children who are household contacts of an infected individual and therefore at high risk for SARS-CoV-2 infection.

For more details, refer to the IB.

#### 4. ENDPOINTS

Endpoints are specified for study cohorts (as defined in Section 6.1.6).

Symptomatic SARS-CoV-2 infection is determined by a positive central lab SARS-CoV-2 RT-qPCR result during the EAP with signs/symptoms occurring within  $\pm 14$  days of a positive RT-qPCR.

The “strict-term”, “broad-term” and CDC definitions for signs/symptoms of SARS-CoV-2 infection is presented in Section 9.2.2.2.

#### 4.1. Cohort A and Cohort A1: SARS-CoV-2 RT-qPCR Negative at Baseline

The endpoints are for subjects who are seronegative at baseline (based on central lab test), unless stated otherwise.

##### 4.1.1. Cohort A Primary Endpoints

###### *Cohort A Primary Efficacy Endpoint*

- Proportion of subjects who have a symptomatic RT-qPCR confirmed SARS-CoV-2 infection (broad-term) during the EAP

###### *Cohort A and Cohort A1 Primary Safety Endpoints*

- Proportion of subjects with TEAEs and severity of TEAEs

##### 4.1.2. Cohort A Key Secondary Endpoints

- Proportion of subjects with viral load  $>4$  ( $\log_{10}$  copies/mL) in NP swab samples during the EAP
- Number of weeks of symptomatic RT-qPCR confirmed SARS-CoV-2 infection (broad-term) during the EAP
- Number of weeks of high viral load  $>4$  ( $\log_{10}$  copies/mL) in NP swab samples during the EAP
- Number of weeks of RT-qPCR confirmed SARS-CoV-2 infection (regardless of symptoms) during the EAP
- Proportion of subjects who have a RT-qPCR confirmed SARS-CoV-2 infection (regardless of symptoms) during the EAP
- Proportion of subjects in placebo group with a RT-qPCR confirmed SARS-CoV-2 infection during the EAP with an index case participating in study R10933-10987-COV-2067 (comparison of those whose index cases receive REGN10933+REGN10987 versus placebo in study R1033-10987-COV-2067)

##### 4.1.3. Cohort A and Cohort A1 Other Secondary Endpoints

- Proportion of subjects who have a symptomatic RT-qPCR confirmed SARS-CoV-2 infection (CDC definition) during the EAP
- Number of weeks of symptomatic RT-qPCR-confirmed SARS-CoV-2 infection (CDC definition) during the EAP
- Proportion of subjects who have a symptomatic RT-qPCR confirmed SARS-CoV-2 infection (strict-term) during the EAP
- Number of weeks of symptomatic RT-qPCR-confirmed SARS-CoV-2 infection (strict-term) during the EAP

- Proportion of subjects who have a RT-qPCR confirmed SARS-CoV-2 infection at each week in the EAP
- Proportion of subjects who have a symptomatic RT-qPCR confirmed SARS-CoV-2 infection (broad term) at each week in the EAP
- Time-weighted average of viral load ( $\log_{10}$  copies/mL) from the first positive SARS-CoV-2 RT-qPCR in NP swab samples (that has an onset during the EAP) until the third weekly visit after the first positive test during the EAP (*Note: Only for RT-qPCR positive subjects during the EAP in the seronegative modified full analysis set for cohort A [seronegative mFAS-A]*)
- Time-weighted average of viral load ( $\log_{10}$  copies/mL) from the first positive SARS-CoV-2 RT-qPCR in NP swab samples (that has an onset during the EAP) until the second weekly visit after the first positive test during the EAP (*Note: Only for RT-qPCR positive subjects during the EAP in the seronegative mFAS-A*)
- Maximum SARS-CoV-2 RT-qPCR viral load ( $\log_{10}$  copies/mL) in NP swab samples among individuals with  $\geq 1$  RT-qPCR positive that has an onset during the EAP
- SARS-CoV-2 RT-qPCR viral load ( $\log_{10}$  copies/mL) in NP swab samples corresponding to the onset of first positive RT-qPCR during the EAP
- Area under the curve (AUC) in viral load ( $\log_{10}$  copies/mL) from the first positive SARS-CoV-2 RT-qPCR NP swab samples detected during the EAP until the first confirmed negative test (testing that occurs after the EAP will be included if necessary to achieve a negative test result) (*Note: Only for RT-qPCR positive subjects during the EAP in the seronegative mFAS-A*)
- Number of medically attended visits in emergency rooms or urgent care centers related to a RT-qPCR confirmed SARS-CoV-2 infection that has an onset during the EAP
- Proportion of subjects with at least 1 COVID-19-related hospitalization or emergency room visit associated with a positive RT-qPCR during the EAP, or all-cause death
- Proportion of subjects requiring medically attended visits in emergency rooms or urgent care centers related to a RT-qPCR confirmed SARS-CoV-2 infection that has an onset during the EAP
- Proportion of subjects hospitalized related to a RT-qPCR confirmed SARS-CoV-2 infection that has an onset during the EAP
- Number of days of hospital and intensive care unit (ICU) stay in subjects hospitalized for a RT-qPCR confirmed SARS-CoV-2 infection that has an onset during the EAP
- Number of days missed for daily responsibilities (where applicable), including work (employed adults) or school (students), daycare or family obligations/responsibilities (childcare or eldercare) due to a RT-qPCR confirmed SARS-CoV-2 infection that has an onset during the EAP
- Proportion of subjects in the placebo group with a RT-qPCR confirmed SARS-CoV-2 infection during the EAP with at least 1 household member participating either in study R10933-10987-COV-2067 or in cohort B (comparison of those whose households

members receive REGN10933+REGN10987 versus placebo in study R1033-10987-COV-2067 or in cohort B)

#### ***Additional Cohort A1 Secondary Efficacy Endpoint***

- Proportion of subjects who have a symptomatic RT-qPCR confirmed SARS-CoV-2 infection (broad-term) during the EAP.
- Proportion of subjects with viral load  $>4$  (log10 copies/mL) in NP swab samples during the EAP
- Number of weeks of symptomatic RT-qPCR confirmed SARS-CoV-2 infection (broad-term) during the EAP
- Number of weeks of high-viral load  $>4$  (log10 copies/mL) in NP swab samples during the EAP
- Number of weeks of RT-qPCR confirmed SARS-CoV-2 infection (regardless of symptoms) during the EAP
- Proportion of subjects who have a RT-qPCR confirmed SARS-CoV-2 infection (regardless of symptoms) during the EAP
- Proportion of subjects in placebo group with a RT-qPCR confirmed SARS-CoV-2 infection during the EAP with an index case participating in study R10933-10987-COV-2067 (comparison of those whose index cases receive REGN10933+REGN10987 versus placebo in study R1033-10987-COV-2067)

#### ***Cohort A and Cohort A1 Safety Endpoints***

- Proportion of baseline seropositive subjects (based on central lab test) with TEAEs and severity of TEAEs
- Incidence and severity of symptomatic SARS-CoV-2 infection in seronegative and seropositive subjects (based on central lab test) in both the EAP and follow-up periods

#### ***Cohort A and Cohort A1 Pharmacokinetic and Immunogenicity Endpoints***

- Concentrations of REGN10933 and REGN10987 in serum over time and selected PK parameters in both seronegative and seropositive subjects (based on baseline central lab test)
- Immunogenicity as measured by ADAs and NAbs to REGN10933 and REGN10987 over time in both seronegative and seropositive subjects (based on baseline central lab test)

#### **4.1.4. Cohort A and Cohort A1 Exploratory Endpoints**

The exploratory endpoints for cohort A are:

- Proportion of baseline-seronegative subjects who have a first RT-qPCR confirmed SARS-CoV-2 infection in the follow-up period (ie, after day 29 visit)
- Proportion of baseline seronegative subjects who become seropositive (based on central lab test) up to day 57

- Proportion of baseline-seropositive subjects (based on central lab test) who subsequently have a positive SARS-CoV-2 RT-qPCR and symptomatic (strict-term) SARS-CoV-2 infection during the EAP
- Proportion of subjects with negative RT-qPCR (based on central lab test) regardless of the serology status at baseline who subsequently have a positive SARS-CoV-2 RT-qPCR and symptomatic (strict-term) SARS-CoV-2 infection during the EAP
- Proportion of baseline-seronegative or baseline-seropositive subjects with negative RT-qPCR (based on central lab test) who subsequently have a positive SARS-CoV-2 RT-qPCR and symptomatic (strict-term) SARS-CoV-2 infection during EAP
- Proportion of baseline-seropositive subjects (based on central lab test) who subsequently have a positive SARS-CoV-2 RT-qPCR and symptomatic (broad-term) SARS-CoV-2 infection during the EAP
- Proportion of subjects with negative RT-qPCR (based on central lab test) regardless of the serology status at baseline who subsequently have a positive SARS-CoV-2 RT-qPCR and symptomatic (broad-term) SARS-CoV-2 infection during the EAP
- Proportion of baseline-seronegative or baseline-seropositive subjects with negative RT-qPCR (based on central lab test) who subsequently have a positive SARS-CoV-2 RT-qPCR and symptomatic (broad-term) SARS-CoV-2 infection during the EAP
- Proportion of baseline-seropositive subjects (based on central lab test) who subsequently have a positive SARS-CoV-2 RT-qPCR and symptomatic (CDC definition) SARS-CoV-2 infection during the EAP
- Proportion of subjects with negative RT-qPCR (based on central lab test) regardless of the serology status at baseline who subsequently have a positive SARS-CoV-2 RT-qPCR and symptomatic (CDC definition) SARS-CoV-2 infection during the EAP
- Proportion of baseline-seronegative or baseline-seropositive subjects with negative RT-qPCR (based on central lab test) who subsequently have a positive SARS-CoV-2 RT-qPCR and symptomatic (CDC definition) SARS-CoV-2 infection during the EAP
- Proportion of baseline-seropositive subjects (based on central lab test) who subsequently have a positive SARS-CoV-2 RT-qPCR during the EAP
- Time-weighted average of viral load ( $\log_{10}$  copies/mL) from the first positive SARS-CoV-2 RT-qPCR in NP swab samples (that has an onset during the EAP) until third weekly visit after the first positive test in seropositive subjects (based on central lab test) during the EAP
- Time-weighted average of viral load ( $\log_{10}$  copies/mL) from the first positive SARS-CoV-2 RT-qPCR in NP swab samples (that has an onset during the EAP) until the second weekly visit after the first positive test in seropositive subjects (based on central lab test) during the EAP
- Area under the curve (AUC) in viral load ( $\log_{10}$  copies/mL) in NP swab samples from the first positive SARS-CoV-2 RT-qPCR NP swab sample until the first confirmed

negative test, in seropositive subjects (based on central lab test) that has an onset during the EAP

- Proportion of subjects in the placebo group who have a RT-qPCR confirmed SARS-CoV-2 infection (regardless of symptoms) during the EAP by the status of household members participating in study R10933-10987-CoV-2067 and receiving REGN10933+REGN10987 or whose household member did not receive treatment with REGN10933+REGN10987
- Proportion of subjects who have a RT-qPCR confirmed SARS-CoV-2 infection (regardless of symptoms) during the EAP by the status of household members participating in study R10933-10987-CoV-2067 and receiving REGN10933+REGN10987
- Proportion of subjects who have a RT-qPCR confirmed SARS-CoV-2 infection (regardless of symptoms) during the EAP by the status of household members receiving an approved monoclonal antibody treatment for COVID-19
- Proportion of subjects who have a RT-qPCR confirmed SARS-CoV-2 infection (regardless of symptoms) during the EAP by the status of household members receiving an approved monoclonal antibody treatment for COVID-19 or REGN10933+REGN10987 in study R10933-10987-CoV-2067
- Maximum RT-qPCR viral load ( $\log_{10}$  copies/mL) in NP swab samples during the EAP in subjects who have asymptomatic infection during the EAP
- Maximum RT-qPCR viral load ( $\log_{10}$  copies/mL) in NP swab samples during the EAP in subjects who have symptomatic infection during the EAP
- Maximum RT-qPCR viral load ( $\log_{10}$  copies/mL) in NP swab samples during the EAP in subjects who have a medically attended visit

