- Proportion of subjects requiring medically attended visits in emergency rooms or urgent care centers related to a RT-qPCR confirmed SARS-CoV-2 infection at baseline or during the EAP, according to baseline serology test status (ie, seropositive or other, based on central lab test)
- Proportion of subjects hospitalized related to a RT-qPCR confirmed SARS-CoV-2 infection at baseline or during the EAP, according to baseline serology test status (ie, seropositive or other, based on central lab test)
- Number of days of hospital and ICU stay in subjects hospitalized for a RT-qPCR confirmed SARS-CoV-2 infection at baseline or during the EAP, according to baseline serology test status (ie, seropositive or other, based on central lab test)
- Number of days missed for daily responsibilities (where applicable), including work (employed adults) or school (students), or family obligations/responsibilities (childcare or eldercare) due to a RT-qPCR confirmed SARS-CoV-2 infection at baseline or during the EAP, according to baseline serology test status (ie, seropositive or other, based on central lab test)
- Maximum RT-qPCR viral load ( $\log_{10}$  copies/mL) in NP swab samples during the EAP in subjects who have asymptomatic infection during EAP
- Maximum RT-qPCR viral load ( $\log_{10}$  copies/mL) in NP swab samples during the EAP in subjects who have symptomatic infection during EAP
- Maximum RT-qPCR viral load ( $\log_{10}$  copies/mL) in NP swab samples during the EAP in subjects who have a medically attended visit related to a RT-qPCR confirmed SARS-CoV-2 infection at baseline or during the EAP

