4.5.4. Cohort A and Cohort A1 Exploratory Efficacy Variables

The following exploratory variables are for both Cohort A and Cohort A1. Some of the endpoints will mature and be assessed after all subjects complete the study. For continuous variables the analysis only applies to subjects who have a positive central lab SARS-CoV-2 RT-qPCR test (based on observed data) during the EAP.

Exploratory Variables	Type
Proportion of baseline-seronegative subjects who have a first RT-qPCR confirmed SARS-CoV-2 infection in the follow-up period (i.e. after Day 29 visit)	B
Proportion of baseline-seronegative subjects who become seropositive (based on central lab test) up to day 57 (Note: For post-treatment serology, only antibody assay(s) that do not bind to REGN10933 or REGN10987 will be used to define the endpoint)	B
Proportion of baseline-seropositive subjects (based on central lab test) who subsequently have a positive SARS-CoV-2 RT-qPCR and symptomatic (strict-term) SARS-CoV-2 infection during the EAP	B
Proportion of subjects with negative RT-qPCR (based on central lab test) regardless of the serology status at baseline who subsequently have a positive SARS-CoV-2 RT-qPCR and symptomatic (strict-term) SARS-CoV-2 infection during the EAP	B

Proportion of baseline-seronegative or baseline-seropositive subjects with negative RT-qPCR (based on central lab test) who subsequently have a positive SARS-CoV-2 RT-qPCR and symptomatic (strict-term) SARS-CoV-2 infection during the EAP	B
Proportion of baseline-seropositive subjects (based on central lab test) who subsequently have a positive SARS-CoV-2 RT-qPCR and symptomatic (broad-term) SARS-CoV-2 infection during the EAP	B
Proportion of subjects with negative RT-qPCR (based on central lab test) regardless of serology status at baseline who subsequently have a positive SARS-CoV-2 RT-qPCR and symptomatic (broad-term) SARS-CoV-2 infection during the EAP	B
Proportion of baseline-seronegative or baseline-seropositive subjects with negative RT-qPCR (based on central lab test) who subsequently have a positive SARS-CoV-2 RT-qPCR and symptomatic (broad-term) SARS-CoV-2 infection during the EAP	B
Proportion of baseline-seropositive subjects (based on central lab test) who subsequently have a positive SARS-CoV-2 RT-qPCR and symptomatic (CDC definition) SARS-CoV-2 infection during the EAP	B

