The secondary and exploratory continuous efficacy endpoints such as TWA, AUC, and maximum viral load (\log_{10} copies/mL) will be analyzed using the ANOVA including treatment group, region, and age group as fixed effects in the model. The continuous endpoints regarding change from baseline in cohort B (e.g., TWA of change/percent change from baseline) will be analyzed using the ANCOVA model with treatment group, region, and age group as fixed effects, and the relevant baseline values as covariate as well as treatment-by-covariate interaction. The REGN10933+REGN10987 group will be compared to the placebo group and corresponding least square of mean difference, standard error (SE) and 95% confidence interval will be provided. For

other endpoints with non-normal/skewed distribution (e.g. number of days of symptoms (strict-term, and CDC definition, etc.)), Van Elteren test will be used.

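### The SAP's treatment ANOVA covers peak viral load within infection subgroups defined by symptoms after dosing; these exploratory contrasts are not randomized comparisons and may understate the drug's benefit

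*Protocol*

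**What the plan says.** - Protocol 4.1.4 (cohorts A and A1; also SAP 4.5.4) defines three exploratory endpoints for maximum viral load: "in NP swab samples during the EAP in subjects who have asymptomatic infection during the EAP"; "in NP swab samples during the EAP in subjects who have symptomatic infection during the EAP"; and "in NP swab samples during the EAP in subjects who have a medically attended visit".
- Protocol 4.2.4 (cohorts B and B1; also SAP 4.5.8) repeats them: "in NP swab samples during the EAP in subjects who have asymptomatic infection during EAP"; "in NP swab samples during the EAP in subjects who have symptomatic infection during EAP"; and a third for visits related to the infection.
- For continuous exploratory variables in cohorts A and A1, SAP 4.5.4 states that "the analysis only applies to subjects who have a positive central lab SARS-CoV-2 RT-qPCR test (based on observed data) during the EAP".
- SAP 5.7.4, under continuous endpoints, names maximum viral load among the secondary and exploratory endpoints that "will be analyzed using the ANOVA including treatment group, region, and age group as fixed effects in the model". It then calls for a comparison of drug with placebo by least-squares mean difference, standard error and 95% confidence interval. Protocol 11.4.3.3 gives the same model family.
- Both sections allow nominal p-values. Neither says that these subgroup contrasts are non-randomized.
- Protocol 5.2 defines asymptomatic infection as a positive swab with none of the listed symptoms in the efficacy assessment period (EAP).
- Protocol 4.1.3 has a related other secondary endpoint: "Number of days of hospital and intensive care unit (ICU) stay in subjects hospitalized for a RT-qPCR confirmed SARS-CoV-2 infection". Protocol 4.2.3 has the cohort B counterpart.

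**The concern.** Whether an infected subject ends up asymptomatic or symptomatic is decided after randomization, and preventing symptoms is the primary objective in both cohorts. If the drug stops symptoms in people who would otherwise have had them, the active asymptomatic group contains subjects whose placebo counterparts sit in the symptomatic group. The two asymptomatic groups then differ in who is in them as well as in treatment, and a treatment term in an ANOVA does not repair that. In cohort A the restriction to subjects who became PCR positive adds a second selection on an outcome that the drug changes.

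What is at stake is the reading of an exploratory table: a mean difference with a confidence interval and possibly a p-value, presented as an estimate of the drug's effect on viral load when part of it may be selection. Hospital and ICU days among those hospitalized have the same structure, and a death shortens the stay.

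**Working it through.** **1. Does the drug change the subgroups?** Protocol 3.2.5 reports symptomatic infection in 8/223 (3.6%) placebo and 0/186 active subjects, odds ratio 0.00 (0.00, 0.69), p<0.01. Fisher's exact test gives p = 0.0091 and the exact upper limit is 0.689, so the stated figures reproduce. For symptom status the answer is yes. For medically attended infections the documents give no data; an effect there is only an objective.

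**2. What the counts allow.** Protocol 3.2.6 reports load above 4 log10 in 13/21 (62%) infected placebo and 0/9 infected active subjects. Assume the 8 symptomatic placebo subjects are among the 21, and let k of them have high load. The placebo asymptomatic group then has 21 − 8 = 13 subjects, of whom (13 − k)/13 have high load:

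| k | 0 | 4 | 5 | 6 | 7 | 8 |
|---|---|---|---|---|---|---|
| Placebo asymptomatic, high load | 100% | 69% | 62% | 54% | 46% | 38% |

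The value without selection is 62%, so k = 5 gives almost no bias. Values of 6 to 8 (load tracks symptoms) lower the placebo figure and bias against the drug; values of 0 to 4 bias in its favour. The documents do not give k. The counts may also come from different sets: 10.3% of 223 at day 8 is about 23 infected, more than 21.

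**3. Size of the bias with no drug effect on load.** Simulation assumptions, none from the documents except the two shares: normal maximum load, SD 1.5 to 2.5 log10, mean set so that 13/21 exceed 4; odds of symptoms multiplied by 1.25 to 2.0 per log10; placebo symptomatic share 8/21. Active minus placebo, log10:

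| Symptomatic infections left by the drug | Asymptomatic group | Symptomatic group |
|---|---|---|
| none | +0.19 to +1.07 | not estimable |
| 20% | +0.15 to +0.82 | +0.15 to +1.37 |
| 50% | +0.09 to +0.50 | +0.09 to +0.72 |

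Both groups can show a false rise together. With 624 per arm, infection 10% versus 5% (assumed), SD 2, all symptoms removed and a two-sample t-test, the asymptomatic contrast had the wrong sign in 89% of trials (odds ratio 1.5) to 97% (odds ratio 2.0). It was nominally significant for a rise in 22% to 45%.

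**4. Against the reported effect.** Protocol 3.2.6 says peak load was on average more than 100-fold higher in placebo infections, that is, more than 2 log10. If the bias simply adds, a true 2 log10 reduction would appear as 2 − 1.07 = 0.93 to 2 − 0.19 = 1.81 log10: smaller, with the right sign. On the counts, no active subject was symptomatic, so all 9 active infections were asymptomatic and none had high load. The asymptomatic contrast is 0% against at least 38% for every k.

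**5. Estimability.** If 0/186 recurs, the cohort A symptomatic contrast has no active subjects, and SAP 5.7.4 gives no fallback.

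**6. A contrast that keeps the randomized groups.** Over all seronegative subjects in the assessment, high load is 13/223 (5.8%) versus 0/186, assuming load was available for all. Apart from its requirement of at least one post-baseline load, this is the first cohort A key secondary endpoint.

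**The case against.** The strongest reply is that the plan already treats these endpoints lightly. They are exploratory and outside the testing hierarchy, and p-values are nominal and optional. Protocol 11.4.3.3 calls descriptive statistics the primary approach, SAP 5.7.4 applies key secondary methods to exploratory endpoints only where appropriate, and cohorts A1 and B1 have no hypothesis testing. The viral-load claims under error control (proportion above 4 log10 and weeks of high load in cohort A, weeks of high load in cohort B) do not condition on infection or symptoms after randomization. For hospital stay, the plan also has the proportion hospitalized and a composite that includes all-cause death.

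All of this stands, and it sets the weight of the point. It does not remove it: the general descriptive wording does not override the specific sentence that sends exploratory maximum viral load to a between-arm ANOVA.

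A reader might infer something stronger: that the plan will show the drug raising viral load. The documents do not support that. A reversal needs a drug that prevents symptoms but hardly changes load, whereas the administrative data show 0/9 versus 13/21 with high load and more than 100-fold higher placebo peaks. The direction of bias also rests on load tracking symptoms, for which the documents give no figure.

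**Conclusion.** The point holds as a minor one. As written, SAP 5.7.4 makes between-arm comparisons of maximum viral load in groups defined by an outcome that the drug is meant to change and, for symptoms, did change. They are not randomized comparisons. If higher load goes with symptoms, they are biased against the drug, by about 0.2 to 1.1 log10 in asymptomatic infections under the simulation's assumptions when all symptoms are prevented. Given the reported reduction, understating the benefit is the likely consequence; a change of sign is possible only if the true effect on load is small. The cohort A symptomatic contrast may not be estimable at all. For medically attended infections, and for hospital and ICU days, the weakness is structural, because no drug effect on those outcomes has been shown. No primary or key secondary result, sample size or error rate is affected.

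**What to change.** - In SAP 5.7.4, exclude the three subgroup endpoints in cohorts A and B from the treatment ANOVA. Present maximum viral load by symptom status and by medically attended visit descriptively within each arm, which still shows whether load tracks symptoms.
- Rest between-arm viral-load conclusions on existing endpoints that do not condition on infection or symptoms after randomization. In cohort A these are the proportion above 4 log10 and weeks of high load. In cohort B they are weeks of high load and maximum load over all of the seronegative mFAS-B, where everyone is infected at baseline.
- Add a note that maximum load among infected cohort A subjects (Protocol 4.1.3) also conditions on a post-randomization outcome that the drug changes. It should not serve as the clean alternative.
- Report hospital and ICU days over the whole analysis set, with 0 for subjects not hospitalized and deaths shown alongside.

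The cost is SAP wording and slightly different tables, with no new data. The loss is a set of nominal p-values in exploratory subgroups.
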